	gamma globulins, or anticonvulsive drugs within the				
	previous 6 months.				
Endpoints	Primary Endpoint: Cumulative number of RTIs over the 12				
	months.				
	monuis.				
	Secondary Endpoints:				
	• Duration in days of RTIs				
	• Antibiotic use (n. of cycles and days)				
	Missed school/work days				
	• Adenoid and tonsil survey (described in appendix 1 of the				
	original protocol)				
	• Size of adenoid tissue over the 12 months according to				
	radiographic and flexible nasopharyngoscopic evaluation (described				
	in appendix 3 of original protocol).				
	Surgery need				
	• AEs				
	Patients will be recruited from 01 September 2017 to 01 March				
Procedures	2018. The trial will begin in 01 September 2017 and will be				
	completed 01 March 2019.				
	Children with the ages of 2-6 years who have recurrent RTIs and				
	AH will be evaluated for the eligibility for the study. When eligible				
	for the study, children's all demographic characteristics will be				
	recorded (Table 1). Eligible children will be evaluated by ear-nose-				
	throat (ENT) specialist and flexible laryngoscopy and radiographic				
	evaluation of adenoid size will be performed in order to measure the				
	adenoid size. All children will be evaluated by an allergy specialist.				
	Complete blood count, serum IgG, IgA, IgE, IgM will be measured.				

Skin prick test will be performed with common allergens.

All children will be randomized into two study arms (active treatment and placebo). OM-85 3.5 mg capsule or placebo will be given according to the standard treatment schedule (10-10-10) for the three consecutive months. All patients will receive 2 cures of treatment at the beginning and 6 Months after inclusion in the study. Every patients will be followed-up for 12 months.

Patients (and care giver/parents) will be given a symptom score form (Table 2) in order to record all nasal symptoms, signs and duration of RTIs, antibiotic use, days of absenteeism from school and from work for family members, monthly.

All patients will be asked to come to the clinic when they have symptoms of RTI in order to diagnose the type of RTIs. Then they will be asked to complete the infection form during the acute RTIs (Table 3).

Every 3 months they will fill in the Tonsil and Adenoid Health Status Survey (Table 4).

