Appendix 1. Study Forms

Table 1. Demographic charecteristics

PATIENT FOLLOW-UP FORM		
Date		
Patient Number		
Treatment group (Randomisation code)		
Name Surname		
Birth date		
Gender		
Smoking at home		
Family history of asthma		
Family history of atopy		
DPT		
lgG		
IgA		
lgE		
IgM		
FIRST VISIT		
RTIs in previous 12 months		
RTIs in previous 6 months		
Number of hospitalisation in previous 12 months		
Total days of hospitalisation in previous 12 months		
Total days of absenteisim from school		
Total days of absenteisim from work for mother		
Total days of absenteisim from work for father		
Antibiotic use in previous 12 months		
Number of box		
Total number of days		
Symptome score		

QoLQ (Score)	
Adenoid size	
Radiological (AC/SP ratio)	
Nasopharingoscope (perceived percent obstruction of the choana)	

Table 2. Symptomes score (will be completed for each month)

Symptomes	none (0 point)	rarely (1 point)	frequently (2 points),	constantly (3 points)
Snoring				
mouth breathing awake				
mouth breathing asleep				
nasal congestion				
hyponasal voice				
chronic nasal discharge				
daytime drowsiness, or hyperactivitiy				
restless sleep				
sleep apnea <15 sec				
night cough				
poor oral intake/weight loss				

Scores from eleven symptoms were added together to provide a total symptom score of 33.

Table 3. Infection form (will be completed for each infection)

Type of RTI	
Duration of RTI	
Antibiotic consumption (days)	
Days of absenteism from school	
Days of absenteism from work for family members	

Table 4. Tonsil and Adenoid Health Status Survey (It will be completed by the parents in every
3 months)

TONSIL AND ADENOID SURVEY

We are conducting a study on children with tonsil or adenoid problems, and we are interested in the type of health problems that your child is having related to his (her) tonsils and adenoids. There are no correct or incorrect answers, and your opinion is most important to us. The survey is completely voluntary and will take about 3 minutes to complete.

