Please answer these questions remembering the past 6 months for your child. The questions relate to the problems many children have related to their tonsils and adenoids. If a certain question is not a problem for your child, please circle "0" (not a problem) for that question. Please do not skip questions or leave any questions unanswered.

.....

Over the past 6 months, how much of a problem were the following conditions for your child?

Please circle the most correct response

		Nict a problem	very mild problem		fairly bad problem	severe problem	
1.	Snoring loudly during sleep	0	1	2	3	4	1
2.	Strep throat infections	0	1	2	3	4	2
3.	Many trips to a doctor's office	0	1	2	3	4	3
4.	Taking antibiotics for more than 3 weeks straight	0	1	2	3	4	4
5.	Taking antibiotics over and over for less than 2 weeks at a time	0	1	2	3	4	5
6.	Many calls to a doctor's office	D	1	2	3	4	8
7.	Irregular or stopped breathing, also known as apnea, during sleep	D	1	2	3	4	,
8.	Repeated short-term (or acute) infections of the tonsils that last less than 2 weeks	D	1	2	3	4	a
9.	Constant, or chronic, infection of the tonsils that last more than 2 weeks	D	1	2	3	4	9
0.	The cost of medical care and prescriptions	D	1	2	3	4	16
1.	Breathing through the mouth during the day	0	1	2	з	4	11
2.	Your child not growing or gaining weight as expected	0	1	2	з	4	12
13.	Noisy breathing during the day	D	1	2	3	4	12
4.	Problems with poor appetite or poor eating habits	0	1	2	3	4	14
5.	Behavior problems at home or at school, or poor school grades or reports	0	1	2	3	4	11

Table 5. Follow-up form

Visit (3-6-9-12 months)	Date:					
Number of RTIs in previous 3 months:						
• Туре	AOM	AS	AT	AN	AC	Р

Number					
Duration (days)					
Antibiotic use in previous 3 months					
• Туре					
Number (box)					
Duration (days)					
Hospitalisation:	(((($\overline{(0)}$	$\overline{(1111)}$	(((($\overline{(00)}$
Number					
Duration (days)					
Symptome score					
QoLQ (Score)					
Adenoid size					
Radiological (AC/SP ratio)					
 Nasopharingoscope (perceived percent obstruction of the choana) 					

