Statistical method:

All analyses will be performed with a commercially available software program (SPSS Statistical Software, version 11.5; SPSS, Inc, Chicago, Ill). The Shapiro-Wilks test will be used to evaluate normality of the distributions collected. When variables were normally distributed, they were expressed as means (SDs); otherwise, they will be expressed as medians and interquartile ranges (25th-75th percentiles). The χ^2 test will be used for categorical variables and expressed as observation counts (in percentages). An ANOVA (or Mann-Whitney U depending on the normality of data) statistics will be used to compare means between both treatment groups for continuous variables. Bonferroni multiple comparison test will be used to compare paired intervals (0-3, 0-6 months). All P values are 2-tailed; a P value of less than .05 are considered statistically significant.

Sample Size:

In one study OM-85 group showed 3 less RTIs compared with placebo over 12 months period. A sample size of 54 randomized patients (27 per group) will provide at least 80% power to detect a mean difference of at least 2.0 RTIs between the two groups assuming a SD of 2.55 and assuming a drop-rate of 20% after 6 months, total of 68 patients (34 per group) will be recruited to the study.¹

Reference:

María Dolores Gutiérrez-Tarango and Arturo Berber. Safety and Efficacy of Two Courses of OM-85 BV in the Prevention of Respiratory Tract Infections in Children During 12 Months. CHEST 2001; 119:1742–1748

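### Antibiotic days are compared between arms without the previous-12-month antibiotic days already recorded at the first visit: a valid test that may give up precision on a secondary endpoint

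*SAP*

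**What the plan says.** The Protocol (Objectives, Endpoints) lists reduction of antibiotic use as a secondary objective, measured in cycles and days. On follow-up, Procedures says "Every patients will be followed-up for 12 months". The follow-up form (Appendix 1, Table 5), completed at months 3, 6, 9 and 12, has the entry "Antibiotic use in previous 3 months", with boxes and duration in days.

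The first-visit part of Table 1 has the entry "Antibiotic use in previous 12 months", with number of boxes and "Total number of days" beneath it. It has no line for cycles.

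The SAP, Statistical method, gives one between-arm procedure: an ANOVA or, if normality fails, a Mann-Whitney U, "used to compare means between both treatment groups for continuous variables". The Protocol's Statistical Methods section says the same in substance. Neither names a covariate, ANCOVA, regression, change score or stratification factor for any endpoint. The Bonferroni comparison of 0-3 and 0-6 months does not use pre-study antibiotic days.

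**The concern.** For antibiotic days, the plan holds a pre-treatment measurement of the endpoint itself: same unit and, for a child who completes follow-up, a window of the same length. Children differ in how many antibiotic days they accumulate. To the extent that this difference persists from the year before entry into the study year, it can be taken out of the comparison. The planned analysis leaves it in the error term or, with Mann-Whitney U, leaves the baseline unused.

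About 27 completers per arm are planned, and the only sample-size calculation is for RTIs, so nothing shows that the trial is adequately powered for antibiotic use. At that size a chance difference between arms in earlier antibiotic use is quite likely. An adjustment chosen only after seeing such a difference would be post hoc; naming it in advance avoids that.

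**Working it through.** **The plan's own figure.** Inputs from SAP, Sample Size: difference 2.0 RTIs, SD 2.55, two-sided alpha 0.05, 27 per arm, 20% dropout. Standardised effect: 2.0/2.55 = 0.784. Noncentrality: 0.784 × √(27/2) = 2.88 on 52 df. Power is 80.7% at 27 per arm and 79.2% at 26, so 27 is the smallest number reaching 80%. Dropout: 27/(1 − 0.20) = 33.75, hence 34 per arm and 68 in total. The stated figures reproduce, and this point does not touch them.

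**Effect of the covariate.** Let ρ be the within-arm correlation of prior-12-month with on-study antibiotic days. It is assumed here, because the documents give no value. ANCOVA residual variance is (1 − ρ²) times the unadjusted variance, interval width scales by √(1 − ρ²), and 27 per arm is worth 27/(1 − ρ²).

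Power uses the noncentral t with effect d/√(1 − ρ²) and 51 df. Two starting points are shown, because no effect size for antibiotic use is stated: the RTI effect borrowed from the sample-size section (d = 0.784, 80.7% unadjusted), and an assumed d = 0.543 (50% unadjusted).

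| ρ (assumed) | Residual variance | Interval width | Equivalent n per arm | Power from 80.7% | Power from 50% |
|---|---|---|---|---|---|
| 0.2 | × 0.96 | × 0.98 | 28.1 | 82.3% | 51.5% |
| 0.3 | × 0.91 | × 0.95 | 29.7 | 84.2% | 53.7% |
| 0.5 | × 0.75 | × 0.87 | 36.0 | 90.4% | 61.8% |
| 0.7 | × 0.51 | × 0.71 | 52.9 | 97.7% | 78.3% |

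From 80.7%, the gain reaches 5 points at ρ of about 0.36.

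**Skewed days and a rank test.** Antibiotic days are likely to be skewed, which would send the SAP to Mann-Whitney U. A simulation compared that test with rank ANCOVA. All settings were assumed: Poisson courses with gamma and lognormal child effects, 7 days per course, baseline mean 5 courses, placebo follow-up mean 3, rate ratio 0.5, 3,000 runs per setting.

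| Spearman correlation | Mann-Whitney U | Rank ANCOVA | Gain (points) |
|---|---|---|---|
| 0.09 | 59.0% | 58.4% | −0.6 |
| 0.25 | 47.4% | 49.1% | +1.7 |
| 0.35 | 39.8% | 43.5% | +3.7 |
| 0.43 | 30.9% | 37.5% | +6.6 |

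Type I error was 4.7% to 5.3%.

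**Chance imbalance.** The difference in baseline means has standard error √(2/27) = 0.27 SD, so an imbalance of at least 0.3 SD in either direction occurs in about 27% of such trials (normal approximation). An unadjusted comparison carries it into the estimate in proportion to ρ: at ρ = 0.5, 0.3 × 0.5 = 0.15 SD of the outcome.

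**The case against.** The strongest reply is that nothing here is wrong. The unadjusted comparison is valid, the endpoint is one of seven secondary ones, and the benefit rests on a correlation nobody has stated. That stands, and it sets the level of the point: an improvement in efficiency.

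There are also reasons to expect a modest correlation. Baseline is a history of the year before entry. On study, symptomatic children are seen at the study clinic under common infection definitions, and Appendix 2 ties antibiotics to named infections, which would tend to even out care-seeking and prescribing. Entry requires at least 3 RTIs in 6 months, which may narrow the baseline range. Recall error lowers the correlation too. These are fair arguments, but they give no value for ρ, and at a low ρ the cost is small as well.

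Three stronger readings are tempting and not supported. A reader might infer that the unadjusted result is biased; randomisation rules that out, and its type I error already allows for chance imbalance. A reader might take 80.7% to 90.4% as the power gain for antibiotic use; that figure combines the RTI effect size with an assumed ρ of 0.5. A reader might say that adjustment takes out known variation and removes imbalance; the baseline is recorded, but its predictive value is unknown, and ANCOVA corrects only the part of an imbalance that is linearly predicted.

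**Conclusion.** The point holds as a possible loss of precision on one secondary endpoint. The facts it rests on are in the documents: antibiotic days are an endpoint, prior-12-month days are recorded before treatment, and no covariate is named. The size is conditional on ρ: negligible at 0.2 or below and material from about 0.4 to 0.5. For a rank analysis of skewed days, expect roughly 0 to 7 points of power under the simulated settings. The direct baseline match is for days only. The equal-window argument applies to completers; a 12-month total is not observed for the 20% expected to drop out.

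**What to change.** Before unblinding, state in the SAP that:

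- antibiotic days on study are compared between arms by ANCOVA with treatment and previous-12-month antibiotic days (Table 1) as covariate, reporting the adjusted difference with its 95% CI;
- where Shapiro-Wilk would lead to Mann-Whitney U, rank ANCOVA with the same covariate replaces it for the p-value only, since ranks give no difference in days;
- for cycles, prior days or boxes may be used as a related covariate, described as such because Table 1 records no cycles;
- children without 12 months of follow-up are handled as in the unadjusted analysis. The statistical sections give no explicit rule for them, and the covariate does not supply one;
- children with no baseline antibiotic record are kept by a simple pre-stated rule, such as imputing the overall baseline mean.

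The cost is this SAP wording, one degree of freedom and the missing-baseline rule. Enrolment, visits, forms and clinical management do not change.

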STUDY PROTOCOL

Effect of Vaxoral[®] (OM-85) on frequency of upper respiratory tract infections and size of adenoid tissue in preschool children with adenoid hypertrophy

Study Product(s)	Vaxoral [®] (OM-85)			
Indication	Recurrent RTIs, adenoid hypertrophy			
Sponsor	[name] Maternity and Children Research and Training			
	Hospital, Department of Pediatric Allergy and Immunology,			
	Ankara, TURKEY			
Anticipated	Taulasa			
Countries	Turkey			
Introduction	OM-85 significantly reduces RTIs in children. This effect was			
	proved by many clinical studies and meta-analyses ¹ . A Cochrane			
	meta-analysis first published in 2006 and updated recently (Del-			
	Rio-Navarro 2012) showed that immunostimulants (IS) could			
	reduce acute RTIs (ARTIs) by almost 39% when compared to			
	placebo. Among the different IS, OM-85 showed the most robust			
	evidence with 4 trials of "A quality" according to the Cochrane			
	grading criteria. Pooling six OM-85 studies, the Cochrane review			
	reported a mean number of ARTIs reduction by -1.20 [95% CI: -			
	1.75, -0.66] and a percentage difference in ARTIs by -35.9% [95%			
	CI: -49.46 , -22.35] compared to placebo ¹ .			
	Adenoid hypertrophy (AH) is one of the most important respiratory			
	disease in preschool children ² . In normal conditions adenoid tissue			
	enlarges up to 5 years and become smaller afterwards. But in some			
	children who have recurrent URTIs, it keeps growing and this can			
	be associated with complications ² . AH may cause recurrent			
	respiratory infections and each infection contributes to enlargement			
	of adenoid tissue thus promoting a vicious cycle. Additionally			
	enlarged adenoids are known to be reservoir for microbes and cause			
	of recurrent or long lasting RTIs ³ .			
	AH is associated with chronic cough, recurrent and chronic			

sinusitis, recurrent tonsillitis, recurrent otitis media with effusion, recurrent other respiratory problems such as, nasal obstruction and sleep disturbances, sleep apneas²⁻³. Eventually, AH causes loss of appetite and growth delay; it is often associated with misuse or over use of antibiotics and often eventually requires surgery. It decreases quality of life both in children and parents and it represents a burden not only for families but also for HCS and society due to increased health cost⁴.

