Every 3 months patients will be asked to come to the clinic and all their records will be collected and they will be evaluated by the ENT specialist for the adenoid tissue size. All these parameters will be recorded in specific forms by the investigator (Table 5).

Patients will be allowed to use nasal corticosteroids, antihistaminic drugs and flu vaccine during the study period and all these study medications will be recorded.

At the end of the study (12 months), immunoglobulin levels will be measured to compare them with basal level.

	1				
Sample Size	A total of 68 patients will be randomized in the study in a 1:1 ratio				
	to Active or Placebo groups.				
	Active group: 34 patients				
	Placebo group: 34 patients				
N ^o Sites					
	Number of study centers: 1				
	Study center: [name] Maternity and Children Research and				
	Training Hospital, Department of Pediatric Allergy and				
	Immunology, Ankara, TURKEY.				
	Study Coordinator and Principal Investigator:				
	[name] M.D. Associate Prof. of Pediatrics and Pediatric				
	Allergy, Training staff on Pediatric Allergy				
	Other Investigators:				
	[name] M.D. Professor of Pediatrics & Subspecialist on				
	Pediatric Allergy and Pediatric Pulmonology				
	Chief of Pediatric Allergy and Immunology Department				
	[name] M.D. Otolaryngologist				
	[name] M.D. Radiologist				
	Statistical method:				
Statistical Methods	All analyses will performed with a commercially available software				
	program (SPSS Statistical Software, version 11.5; SPSS, Inc,				
	Chicago,Ill).				
	The Shapiro-Wilks test will use to evaluate normality of the				
	distributions collected. When variables were normally distributed,				
	they were expressed as means (SDs); otherwise, they will express as				
	medians and interquartile ranges (25th-75th percentiles). The x^2 test				
	will use for categorical variables and expressed as observation				
	counts (in percentages). An ANOVA (or Mann-Whitney U				
	depending on the normality of data) statistics will be used to				
	compare means between both treatment groups for continuous				
	variables. Bonferroni multiple comparison test will use to compared				
	paired intervals (0-3, 0-6 months). All P values are 2-tailed; a P				
	pared intervals (0.5, 0.0 inontins). An 1 values are 2-tailed, a 1				

	value of loss than 05 are considered statistically significant					
	value of less than .05 are considered statistically significant.					

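### The between-arm test for adenoid size and survey score fixes neither a visit nor value or change and leaves the baseline unused, and the only intervals named end by month 6

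*SAP*

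**What the plan says.** **Endpoint and schedule.** The protocol title includes the "size of adenoid tissue in preschool children with adenoid hypertrophy". The Endpoints section lists, as secondary, "Size of adenoid tissue over the 12 months according to" radiographic and nasopharyngoscopic evaluation, together with the tonsil and adenoid survey. Under Procedures, children attend every three months and are "evaluated by the ENT specialist for the adenoid tissue size". Table 1 records adenoid size and survey score at the first visit. Table 5 records both again at months 3, 6, 9 and 12. The second treatment course starts six months after inclusion (Procedures; visit schedule, visit 4).

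**Analysis.** The SAP, Statistical method, contains two relevant sentences. One is a general rule, ANOVA or Mann-Whitney U depending on normality, to "compare means between both treatment groups for continuous variables". The other is "Bonferroni multiple comparison test will be used to compare paired intervals (0-3, 0-6 months"). The Statistical Methods section of the protocol has the same content, including the "paired intervals (0-3, 0-6 months). All P values are 2-tailed; a P" value rule. Neither sentence names a variable.

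**Elsewhere.** One 12-month comparison is described outside the statistical section: "At the end of the study (12 months), immunoglobulin levels will be measured to compare them with basal level". The Sample Size paragraph allows for attrition by "assuming a drop-rate of 20% after 6 months".

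**The concern.** A period of twelve months defines an outcome when the outcome is a count, as with respiratory infections. It does not do so for a size or score measured at four follow-up visits. That result could be the month-12 value, the change from baseline to month 12, the same at another visit, or an average. The plan does not say which, and it applies p<0.05 to everything. Its only named time frames leave out months 9 and 12, the two visits that follow the start of the second course.

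At stake is how the adenoid-size result can be read. If visit and form are settled after the data are seen, a nominally significant result cannot be taken at face value. The choice may also decide how many children are analysed. In addition, a baseline that every child already provides would go unused in a trial of 34 per arm.

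**Working it through.** **1. The plan's own sample size.** Inputs from the SAP, Sample Size: difference 2.0, SD 2.55, 80% power, two-sided 0.05, 20% drop-out.
- Normal approximation: 2 × (1.96 + 0.84)² × 2.55² / 2.0² = 25.5, so 26 per group. The t-test version gives 26.5, so 27.
- 27 / 0.80 = 33.75, so 34 per group and 68 in total. The plan's figures reproduce.
- They concern the infection count only. No variance, effect or correlation is given for adenoid size or the survey.

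**2. Coverage.** Follow-up visits are months 3, 6, 9 and 12. The named intervals end at months 3 and 6, so 2 of 4 visits lie outside them, and both come after the second course starts.

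**3. False-positive chance if the choice is left open.** One measure, no treatment effect, 27 per arm (34 × 0.8 = 27.2), baseline plus four visits, multivariate normal with equal correlation r between visits (assumed), two-sample t-test at two-sided 0.05, 200,000 simulated trials per setting:

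| What is left open | r = 0.9 | r = 0.7 | r = 0.5 |
|---|---|---|---|
| Nothing (month 12, value) | 5.0% | 5.0% | 5.0% |
| Month 12 fixed; value or change open | 9.5% | 9.5% | 9.1% |
| Any of four visits; value only | 9.4% | 13.3% | 15.8% |
| Any of four visits; value or change | 23.1% | 25.9% | 27.1% |

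A separate run of 40,000 trials agreed within simulation error. The second row is plausible on paper: value and change from baseline correlate at √((1 − r)/2), which is 0.22, 0.39 and 0.50 here, so the result sits a little below the independence bound 1 − 0.95² = 9.75%. The bound for four visits is 1 − 0.95⁴ = 18.6%. If correlation instead decays between visits (AR(1)), the third row becomes 10.3%, 14.1% and 16.4%, and the last row 21.4%, 24.1% and 25.4%.

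**4. What the unused baseline is worth.** The effect is borrowed from the infection count, d = 2.0 / 2.55 = 0.784, because none is given for adenoid size. Noncentral t, 27 per arm; r is now the assumed correlation between baseline and month 12.
- Value, unadjusted: d = 0.784, 52 df, power 80.7%. With 34 per arm it is 89.0%.
- Change score: d / √(2(1 − r)) = 0.663, 0.784, 1.013 at r = 0.3, 0.5, 0.7; power 67%, 81%, 95%.
- Analysis of covariance: d / √(1 − r²) = 0.822, 0.906, 1.098, 51 df; power 84%, 90%, 98%.

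Adjustment beats both alternatives at each correlation shown. From about r = 0.5 it recovers the power lost in going from 34 to 27 per arm.

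**5. Three measures at month 12.** For AC/SP ratio, percent choanal obstruction and survey score, each at 0.05, the chance of at least one false positive is at most 1 − 0.95³ = 14.3% if they are independent. It is about 11-14% at assumed correlations of 0.7 to 0.3.

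**The case against.** **The horizon is already twelve months.** The endpoint wording and the length of follow-up make month 12 the natural visit. This has force. If month 12 is accepted, what remains open is value or change, and the relevant figure is 9-10%. Still, no text fixes the visit, and the only time frames in the statistical section point elsewhere.

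**The Bonferroni sentence may not concern adenoid size.** It names no variable and could be meant for other repeated measures, such as the monthly symptom score. That stands. A reader might infer that the plan analyses adenoid size only up to month 6, or deliberately favours early visits. The documents do not support either. A between-arm test exists and covers these measures by type; it lacks a visit and a form.

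**An unadjusted comparison of randomised arms is valid.** Correct. Leaving out the baseline costs precision and is not an error.

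**Attrition.** A reader might infer that 34 per arm are available until month 6 and 27 afterwards. The drop-out phrase may mean losses that occur after month 6, or 20% lost once six months have passed. That 34 remain until then is an assumption.

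**Weight.** These are secondary endpoints. The primary endpoint is a cumulative 12-month count, and nothing here touches it.

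**Conclusion.** The point stands as a gap in the secondary analyses that should be closed. The only named intervals end by the start of the second course. The between-arm test for adenoid size and survey score fixes neither a visit nor value or change, and it leaves the collected baseline unused.

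Its size depends on how much is taken as settled. For one measure it is about 9-10% if month 12 is given, about 9-16% if any one of the four visits may be chosen, and 23-27% only if all four visits and both forms are tested and any significant result is reported. It would be tempting to quote the last range as the plan's error rate, but it is a worst case. All these figures rest on 27 per arm, normal data and assumed correlations. The precision gain, from 81% to 84%, 90% or 98% power, rests on a borrowed effect and assumed baseline correlations of 0.3, 0.5 and 0.7.

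**What to change.** Add to the SAP (Statistical method) and the protocol (Statistical Methods):

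> Adenoid size (AC/SP ratio, percent choanal obstruction) and survey score will be compared between arms at month 12 by analysis of covariance adjusted for the baseline value, as secondary analyses. Comparisons at months 3, 6 and 9 are supportive; the month-3 survey is descriptive because its 6-month recall reaches before treatment. Children who have adenoid surgery before month 12 will be reported by arm, with a sensitivity analysis using their last pre-surgery measurement.

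Also:
- Keep the Bonferroni sentence, but limit it to supportive comparisons against baseline and extend it to 0-9 and 0-12 months. It is the only multiplicity adjustment in either document, so it should be scoped, not deleted.
- Use a rank-based analysis of covariance as a sensitivity analysis, not as a switch triggered by the Shapiro-Wilk test. Used alone on simulated normal data it gave power of 81%, 87% and 96% at baseline correlations of 0.3, 0.5 and 0.7, with type I error of about 5%.

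**Cost.** A short addition to two documents, with no new visits or data. Month 12 is likely to have the fewest children. Three measures at uncorrected 0.05 carry up to a 14% chance of at least one false positive, so they should be read as secondary. Going from two to four intervals lowers the Bonferroni threshold from 0.05/2 = 0.025 to 0.05/4 = 0.0125 for the supportive comparisons.

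**Smallest acceptable change.** Name month 12, and value or change, for the existing between-arm test.
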